Pilot Study: Augmentation of ACL Reconstruction with Bone Marrow Stem Cells and Amnion Collagen Matrix Wrap

Date: 11/27/2017 NCT03294759

Pilot Study: Augmentation of ACL Reconstruction with Bone Marrow Stem Cells and Amnion Collagen Matrix Wrap

Principal Investigators: [name]., [name].

Investigators:
[name], M. D.
[name].
[name].
[name]
[name]

Study Design: Randomized Controlled Trial

No. 1 Background /Scientific Rationale

Histologic studies have determined that graft ligamentization following anterior cruciate ligament (ACL) reconstruction may take from 6 to 18 months. (1) It has been reported that incomplete graft maturation and incorporation is one cause of clinical graft failure. Animal studies have illustrated improved tendon healing/integration in ACL models augmented with stem cell technologies. (2-4). Basic scientists theorize that optimization of stem cell treatments for tissue regeneration requires that a "regenerative triad" be employed, i.e., use of a scaffold, stem cells and growth factors. In the intra-articular environment, research has shown that a scaffold such as an amnion wrap is necessary to contain the stem cells and growth factors in close proximity to the ACL graft. (2, 4, 5)

The normal, uninjured human ACL is covered by a layer of synovial tissue which contributes to the blood supply and nutrition of the native ACL. It is theorized that the lack of a synovial lining after injury and following traditional ACL reconstruction contributes to slow ligamentization and possible failure of reconstructed grafts.(5) Two studies have demonstrated accelerated maturation and ligamentization of human ACL graft augmented with point of care blood products. (6, 7) In one, leucocyte poor platelet rich plasma was injected directly into the body of the graft. (6) In the other, the platelet derived growth factors were loaded in a gelatin carrier which was wrapped around the graft. (7) In both studies accelerated and increased ligament maturation was documented compared to the controls. Collagen membranes derived from amniotic tissue have been successful to aid healing when used in difficult wounds and meniscal repair surgery. (8, 9)

We believe that use of a collagen based -membrane derived from amniotic tissue can be used to help reestablish the natural synovial lining of the reconstructed ACL, in effect acting as both a barrier from the synovial fluid and as a scaffold to contain autologous mesenchymal stem cells and growth factors contiguous with the graft, thus aiding and perhaps accelerating the natural maturation and ligamentization process of the implanted graft tissue. Acceleration and improvement in graft maturation and strength would be a significant advancement in sports medicine allowing safer and earlier return to sports and activity.

No. 2 Objectives

The objective of this study is to evaluate the use of wrapping an ACL graft with a collagen matrix tissue wrap and injecting autologous bone marrow aspirate concentrate under the wrapping and into the graft. We hypothesize that this method of augmenting ACL surgery will accelerate and improve the graft maturation and ligamentization process. We propose to test this hypothesis with a series of cases of ACL reconstructions evaluated with post-operative MRI mapping sequences and validated clinical outcome measures.

No. 3. Subject Eligibility

Inclusion Criteria: Patients between the ages of 18 and 35 who are scheduled to have anterior cruciate ligament reconstruction with autologous grafts by one of the investigating physicians will be screened for participation in this study. Patients must be willing to undergo MRI scans post –operatively at 3, 6, 9 months and 1 year.

Exclusion criteria: Patients with prior procedures or significant prior injuries to the same knee are excluded. Any patient who will have difficulty obtaining internet access, does not have an active e-mail address, or is unable to comprehend study documents or give informed consent will be excluded. Patient who are unable to complete MRI examinations due to claustrophobia or anxiety will be excluded.

No. 4. Subject Enrollment

Patients meeting the inclusion criteria will have the study explained to them by one of the members of the investigating team, and they will be given an opportunity to participate if they are interested. Up to 50 patients who agree to participate will go through the described informed consent process and be enrolled in the SOS registry, which is an IRB approved research database with Baptist Hospital that collects post-surgical outcome surveys. No specific advertising or recruitment material will be utilized.

No. 5. Study Design and Procedures

Study design will be a Level I prospective randomized and blinded trial. Subjects who meet the inclusion criteria will have the study explained in detail and informed consent will be obtained as outlined above. Subjects will be enrolled in the SOS knee arthroscopy registry and complete all pre-operative questions prior to the surgical date either on line or in the office with the assistance of the staff. The patient will complete all routine pre-operative, operative and post-operative protocols for the procedure. An Andrews Institute standard post-operative protocol for the procedure will be followed and physical therapy will be ordered for all participants per normal standard of care. Compliance in physical therapy will be documented.

The study will involve 20 patients undergoing ACL reconstruction with patellar tendon autografts and 20 patients with hamstring autografts for a total of 40 patients. During surgery the grafts will be harvested and prepared in the standard fashion. Patients undergoing ACL reconstruction with patellar and hamstring autografts will be randomized into 2 groups of 10 patients each. One group will have the collagen wrap and stem cell concentrate injection and one will have standard ACL surgery without augmentation of wrap and stem cell injection. All of these procedures are commonly performed at the Andrews Institute and standard protocols will be followed for all procedures. Patients will be blinded to the randomization results.

Bone marrow aspirate will be collected through the surgical site from the distal femur or the iliac crest with a trocar designed for this purpose. Therefore patients will be unable to determine if they have had stem cells harvested. The aspirate will be centrifuged using the Arthrex Angel system (see Appendix 1) to optimally concentrate the cells for implantation. The graft for the experimental groups will be wrapped with a sterile amnion matrix wrap, supplied by Arthrex (see attached Appendix 2), which will be sutured in place. (12) (Fig. 1) The grafts will be implanted and affixed using standard procedure. (Fig. 2) The mesenchymal stem cell concentrate will then be injected under direct visualization inside the collagen matrix wrap and into the graft construct. (Fig.3) A cell count of the stem cell concentrate will be performed prior to implantation to determine quality of the concentrate. After injection any remaining stem cell concentrate will be destroyed. Photographs will be taken to document the delivery of the cells into the graft construct. The grafts for the control groups will be implanted and affixed per normal procedure.

Both groups will be followed utilizing the SOS outcomes system protocol for 2 years. Both groups will undergo post-operative MRI at 3, 6, 9 months and one year utilizing a validated T2 star sequence which will undergo region of interest mapping to produce mean T2 values. (Fig. 4) These values have been shown to detect differences in ACL content, structure and maturation. Mapping will be performed by a blinded musculoskeletal radiologist. After the 12 month MRI, patients will be offered an office needle arthroscopy performed under local anesthesia for the purpose of gross and histological evaluation of their graft. An equal number from each randomized group will be recruited. The goal is to recruit 3 patients from each group, for a total of 12 patients.

No. 6 Expected Risks and Benefits

Risks and Discomforts: There have been no documented risks or side effects from using collagen membranes in human subjects. For patients randomized to the collagen wrap stem cell group, the stem cells will be harvested from either the femur or iliac crest during surgery. This will result in a small needle insertion hole in either the femur or iliac crest for the bone marrow stem cell collection, which will be about the same size as an IV insertion. This may cause some minor pain or swelling and there is a very minor risk of infection. The risks of needle arthroscopy include minor puncture site pain and infection, less than that published for standard arthroscopy. (13) There is a small risk of the exposure of patient's health information, which will be minimized through the rigorous requirements set up in the SOS IRB protocols and the use of subject codes in place of names on all data sheets.

Benefits: Patients may experience accelerated graft maturation as a result of agreeing to participate in the study. Some patients will receive at no extra charge mesenchymal stem cell augmentation of their ACL grafts. Patients will receive follow up MRI scans at no extra charge. Participation in the patient reported outcomes system gives the attending physician the opportunity to remotely monitor patient's health progress and outcomes. Future patients may benefit from the information obtained in this study.

No. 7. Data Management Procedures

All personal information is strictly confidential and no names will be disclosed except as required by law. All data sheets will have names and identifying information replaced with a subject code to protect the confidentiality of the patient. The principal investigator, coinvestigators and research staff will have access to the de-identified data. All subject data forms will be scanned and stored, along with summary information forms and spreadsheets in a secure protected folder on a laptop to which only study investigators will have access. This data will be permanently deleted following any and all publications or presentations have been completed related to this research. All records related to this research will be retained in a secure location for a period of 3 years following the completion of all study related activities, after which time they will be properly destroyed.

No. 8. Data Analysis

The research committee will meet at appropriate intervals to evaluate and analyze the data. The investigators may also access the "Patient Analysis" panel on the SOS website at any time. This allows the investigator to perform comparative analysis on individual outcomes, institutional outcomes and the global de-identified average by choosing filters. De-identified data can be exported in raw data or graphical format.

No. 9. Statistical Considerations

This study will continue to enroll patients until 40 patients complete the study. The data will be arranged in Microsoft Excel spreadsheet format. Ranges, means and standard deviations for all measures will be determined and calculated. Common statistical procedures, such as ANOVA and analysis of covariance will be used to interpret changes in outcome variables from the survey results over time.

No. 10. Quality Control and Assurance

All protocols will be monitored and analyzed data will be checked for accuracy by the principal investigator and /or a designated AREF research team member. All medical data will be kept in compliance with HIPAA guidelines.

No. 11. Regulatory Requirements

Informed Consent: The informed consent process will be performed by one of the study investigators or staff, in the office at the time the decision for surgery is made. All subjects will have the study described to them and will give as much time as they require to read an approved, stamped version of the informed consent document. After signing of the informed

consent document, participants will be given a copy for their records. This process will take place only after the patient has consented to proceed with the surgical procedure.

Subject Confidentiality: Subject confidentiality information is listed above under #7. All medical data will be recorded and stored in compliance with HIPAA guidelines.

No. 12. References

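### Patient blinding is justified only for marrow taken through the knee incision, yet the protocol also allows harvest at the iliac crest, which may reveal the arm

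*Combined protocol and SAP*

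**What the plan says.** Section No. 5 (Study Design and Procedures) makes two unconditional statements about blinding: "Study design will be a Level I prospective randomized and blinded trial" and "Patients will be blinded to the randomization results". In the same section, marrow is to be "collected through the surgical site from the distal femur or the iliac crest", and the conclusion drawn is "Therefore patients will be unable to determine if they have had stem cells harvested".

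Section No. 6 (Expected Risks and Benefits) says who is harvested: "For patients randomized to the collagen wrap stem cell group, the stem cells will be harvested from either the femur or iliac crest during surgery". It describes the puncture, at whichever site is used, as one "which will be about the same size as an IV insertion", and adds: "This may cause some minor pain or swelling and there is a very minor risk of infection".

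Of the two randomized groups within each graft type, section No. 5 says "one will have standard ACL surgery without augmentation of wrap and stem cell injection". It describes no sham puncture, matching dressing or other masking for controls, and no rule for choosing between the two harvest sites.

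**The concern.** The claim that patients cannot tell rests on the puncture being hidden within the operation they know they had. That is reasonable for the distal femur. The iliac crest is at the pelvis. A patient who wakes with a puncture there, perhaps sore, has a sign that no control has.

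The outcomes most exposed are the SOS surveys. They are patient-reported (section No. 6) and run for 2 years (section No. 5), and survey results are the only ones for which section No. 9 names ANOVA and analysis of covariance. Section No. 2 tests the hypothesis with MRI mapping and clinical outcome measures. It does not name SOS, but SOS is the only clinical outcome system the protocol describes. A patient who believes the graft was augmented may answer differently for that reason alone, and nothing in the plan protects the survey answers from this. MRI mapping is better protected because the radiologist is blinded.

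**Working it through.** The protocol gives no figure for this point, so there is none to reproduce. The check is mainly a comparison of statements, followed by a small count.

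**Does the conclusion follow from its premise?**

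| Question | Distal femur | Iliac crest |
|---|---|---|
| Permitted (Nos. 5 and 6)? | Yes | Yes |
| Within the knee operation? | Yes | No |
| Needle hole, possible pain or swelling (No. 6)? | Yes, in the operated region | Yes, away from it |
| Would a control have a similar mark? | Yes, from the knee surgery itself | No, none is described |
| Does the stated ground for blinding apply? | Yes | No |

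Read alone, the harvest sentence in No. 5 names no arm. No. 6 supplies the restriction to the augmented group. The conclusion in No. 5 also presupposes that some patients are not harvested, since otherwise there would be nothing for them to determine.

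**How informative is the cue?**

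Inputs from No. 5: two graft types, each randomized into two groups of 10.

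- Augmented: 2 × 10 = 20.
- Control: 2 × 10 = 20.
- *k* = augmented patients harvested at the crest. It is not stated, so the range is 0 to 20.

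Among patients with a hip puncture, the share who are augmented is *k*/(*k* + 0) = 100% for any *k* of 1 or more.

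Among patients without one, the share who are controls is 20/(20 + 20 − *k*) = 20/(40 − *k*):

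| *k* | Calculation | Share who are controls |
|---|---|---|
| 0 | 20/40 | 50% |
| 5 | 20/35 | 57% |
| 10 | 20/30 | 67% |
| 15 | 20/25 | 80% |
| 20 | 20/20 | 100% |

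The cue is one-sided. A hip puncture settles the question for a patient who understands it. Its absence says little unless crest harvest is common, and a patient would have to know *k* to use it. The exposure is mainly among crest-harvested patients.

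No effect on survey scores is calculated, because the documents give neither *k* nor the size of any expectation effect.

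**The case against.** The strongest reply is that harm is not shown. Crest harvest may never be used. The puncture is small, and the trocar is made for the purpose, so the conclusion in No. 5 may rest partly on how little there is to notice. A patient must notice the mark and also know what it means, and the consent text is not available to show what patients are told. The hypothesis concerns graft maturation, which MRI addresses most directly and which is read blind. This is also a pilot with no declared primary outcome.

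Most of this stands as a limit on the consequence, which is why unblinding is described here as possible and not certain. It does not rescue the inference. The protocol says patients will be unable to tell, and a small, possibly painful puncture at the hip does not support that certainty.

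Two narrower points also have merit. First, the percentages for patients without a puncture describe the cue and do not measure bias. They also assume 20 per arm, although No. 4 allows up to 50 enrolments and No. 9 continues until 40 complete, so the arms could be larger. Second, harvest site is only a proxy for unblinding. Asking patients to guess their assignment would be more direct. That is a sensible addition, but it does not replace recording the site, without which nobody can say whether the problem arose.

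**Conclusion.** The concern holds. As written, the protocol claims patient blinding for everyone, on a ground that covers only one of its two permitted harvest sites. Between 0 and 20 of the 20 planned augmented patients could be exposed. At 0 there is no effect by this route. Above 0, the surveys cannot be reported as fully patient-blinded on the reasoning given, and the size and direction of any bias are unknown.

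This rests on three readings: that harvest is confined to the augmented group, as No. 6 indicates; that no sham or masking is used for controls, since none is described; and that a crest puncture is made away from the knee incision, which anatomy requires. The fault in the reasoning is certain. Its effect on the results is not.

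**What to change.** 1. In No. 5, replace the sentence on patients' ability to tell with: *When marrow is taken from the distal femur through the knee incision, patients are not expected to be able to tell whether it was harvested. This expectation does not extend to harvest at the iliac crest.*
2. In No. 5, qualify the statement of patient blinding: *Patients will not be told their assignment; a patient harvested at the iliac crest may be able to infer it.* Add the same exception where the design is called blinded.
3. Record the harvest site for each augmented patient and report the number of crest harvests.
4. Describe the survey outcomes as fully patient-blinded only if that number is zero. Otherwise describe them as potentially unblinded for the crest-harvested patients.

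The cost is a few sentences, one recorded item per augmented patient, and a less favourable blinding statement.

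Three further steps are for the sponsor to consider. Limiting harvest to the distal femur would remove the problem, but the documents cannot settle its effect on the aspirate. A matching hip dressing for all patients would help at first, but would not hide pain, or the puncture once the dressing is removed. Asking patients to guess their assignment would show whether blinding held, at the cost of one more question.

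### No harm or graft-failure outcome is pre-specified, systematically collected or compared by arm, and enrolling to 40 completers with no rule for failed grafts may leave failures out of the analysis

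*Combined protocol and SAP*

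**What the plan says.** **Why failure and harm matter.** No. 1 states: "It has been reported that incomplete graft maturation and incorporation is one cause of clinical graft failure". No. 6 opens its risk paragraph with "There have been no documented risks or side effects from using collagen membranes in human subjects", then lists minor pain, swelling and a small infection risk from the marrow harvest.

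**What is recorded.** No. 5 sets two main streams of follow-up: "Both groups will undergo post-operative MRI at 3, 6, 9 months and one year", mapped to mean T2 values, and "Both groups will be followed utilizing the SOS outcomes system protocol for 2 years". It also provides for an optional needle arthroscopy with gross and histological assessment after the 12-month scan (goal 12 patients), a cell count of the concentrate, photographs of the injection and documentation of physical therapy compliance. No. 4 describes the SOS registry as collecting outcome surveys after surgery and does not list the items.

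**Who is counted.** No. 5 plans "20 patients undergoing ACL reconstruction with patellar tendon autografts and 20 patients with hamstring autografts for a total of 40 patients"; each graft type "will be randomized into 2 groups of 10 patients each". No. 9 says "This study will continue to enroll patients until 40 patients complete the study". No. 4 sets the ceiling: "Up to 50 patients who agree to participate will go through the described informed consent process".

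**What is analysed.** No. 9 gives ranges, means and standard deviations for all measures, with ANOVA and ANCOVA applied to change in the survey results. No. 8 describes committee review and the SOS analysis panel. No. 10 covers monitoring of protocols and checking of data accuracy. None of these sections mentions adverse events, graft rupture, revision, re-operation or infection as data to be collected or compared.

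**The concern.** The trial adds a tissue wrap, a marrow harvest and an injection to standard surgery in 20 patients. The clinical event that motivates it, graft failure, is not a named outcome, and the harvest-site harms that it foresees have no form, schedule or table. Events that are not collected prospectively, and in the same way in both arms, cannot be reliably rebuilt by an analyst afterwards. The trial would therefore end without a sound basis for checking the low-risk premise in No. 6.

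The completer rule adds a second problem. Once a graft has ruptured or been revised, it can give no later T2 values. The protocol does not say whether such a patient completes the study. One permitted reading is that the patient does not and that another is enrolled. The analysed 40 would then be selected on an outcome that the treatment is meant to influence.

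**Working it through.** **1. The plan's own figures.** 2 graft types × 2 arms × 10 = 40, which reproduces the stated total and gives 20 augmented and 20 control patients. Arthroscopies: 4 groups × 3 = 12, as stated. The ceiling leaves 50 − 40 = 10 possible non-completers, or 10/50 = 20% of those enrolled. No event rate, dropout rate, effect size or power is given, so every event rate below is an assumption.

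**2. Events set against data streams.**
- *Graft rupture or revision:* a rupture might be visible on a scheduled MRI, but the only stated product of the scans is mean T2 values. No rupture or revision outcome is defined.
- *Re-operation and infection:* no stated collection. The SOS items are unknown.
- *Harvest-site complaints:* named as a risk in No. 6, with no stated collection.
- *Arthroscopy and histology:* optional, after 12 months and in about 12 patients, so not a safety outcome for the whole trial.
- *Cell count, photographs, therapy compliance:* recorded, but not safety outcomes.

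**3. What the completer rule permits.** Suppose that k augmented patients fail, are classed as non-completers and are replaced, and that no completer fails. Completers show 0/20 failures, while the randomised rate is k/(20 + k):
- k = 1: 1/21 = 4.8%
- k = 2: 2/22 = 9.1%
- k = 3: 3/23 = 13.0%
- k = 5: 5/25 = 20%

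All of these fit within the ceiling of 50.

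**4. What recording events would deliver with 20 per arm.** The chance of at least one event in an arm is 1 − (1 − p)^20:
- p = 1%: 18%
- p = 2%: 33%
- p = 5%: 64%
- p = 10%: 88%

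Upper limits when no event is seen:
- 20 patients, one-sided 95%: 1 − 0.05^(1/20) = 13.9%
- 20 patients, two-sided exact 95%: 1 − 0.025^(1/20) = 16.8%
- one graft-type cell of 10, one-sided 95%: 1 − 0.05^(1/10) = 25.9%

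Between arms, 0/20 against 4/20 gives Fisher p = 0.106, and 0/20 against 5/20 gives p = 0.047. For assumed rates of 5% and 20%, exact Fisher power is 17%, and 80% power would need about 76 per arm (normal approximation).

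**The case against.** Several stronger readings are tempting, and the documents do not support them.

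- *That the trial records nothing but scans and surveys.* It also records arthroscopy with histology, a cell count, photographs and therapy compliance. None of these is a safety outcome, so the gap remains.
- *That failed grafts are removed and replaced.* No. 9 does not say so. Completion is undefined, a patient with a ruptured graft could still answer surveys to 2 years, and scans taken before the rupture would exist. What stands is that the text permits the loss of failures and has no rule against it.
- *That event data would be wholly absent.* The SOS items are not listed, No. 6 says that the surveys let the physician follow progress remotely, and the scheduled MRIs image the graft four times. Routine charts may hold re-operations and infections. But the protocol commits to no abstraction, no uniform collection and no comparison by arm.
- *That the bias in T2 star can be given a size.* Any such figure needs an assumed failure rate, an assumption that the failed grafts have the worst values, and failures lost from one arm only. With equal expected loss in both arms and no true effect, the expected between-arm bias is zero. The supportable statement is conditional: bias arises if failures differ by arm.

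It is also fair to say that this is a pilot and that event counts from 20 per arm have little power. That limits what the counts can show; it does not justify leaving them uncollected. Worst-rank scoring is one choice among several, and No. 9 does not spell out an arm comparison of T2 star, so it belongs as an optional sensitivity analysis.

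**Conclusion.** The point holds in this form: no harm or graft-failure outcome is pre-specified, systematically collected or compared by arm, although the protocol itself makes graft failure and harvest-site harm relevant. Enrolling to 40 completers, with completion undefined and no rule for a ruptured or revised graft, may let failures fall out of the analysed set. The 0/20 against 2/22 (9.1%) illustration shows the scope for this. It rests on assumed failures, on their being classed as non-completers, and on their replacement. Bias in T2 star follows only if failures differ by arm, and the documents give no basis for sizing it.

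This should be fixed because the cost is small and data not collected uniformly are hard to recover. It does not mean that the trial could establish safety. Even with full recording, no events in 20 treated patients would leave true rates up to 13.9% (one-sided 95%) unexcluded.

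**What to change.** Add to No. 5 and No. 9:

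- For every randomised patient, at the 3, 6, 9 and 12 month MRI visits and with each SOS survey to 2 years, record on one short form: graft rupture or revision, any re-operation, infection, harvest-site complaint and any other adverse event.
- Name graft rupture or revision as an outcome.
- Report counts by randomised arm with exact 95% confidence intervals.
- Define completion. Keep all randomised patients in the comparison, including those with a failed graft and those who do not complete, using their scans from before failure. A worst-rank analysis of T2 star may be added as a sensitivity analysis.
- State that the counts are descriptive, and give the event rate that 20 treated patients can exclude (13.9%, one-sided 95%, if none occurs).

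The cost is a little staff time and one extra table. No visits, procedures or patients are added.

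### No. 2 promises to test an effect on graft maturation, but No. 9 names no augmented-versus-standard difference with its uncertainty, and only descriptive summaries for MRI T2

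*Combined protocol and SAP*

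**What the plan says.** The title calls the study a pilot: "Pilot Study: Augmentation of ACL Reconstruction with Bone Marrow Stem Cells and Amnion Collagen Matrix Wrap". No. 2 (Objectives) then states a directional efficacy hypothesis, "We hypothesize that this method of augmenting ACL surgery will accelerate and improve the graft maturation and ligamentization process", and a plan to test it: "We propose to test this hypothesis with a series of cases of ACL reconstructions evaluated with post-operative MRI mapping sequences". Clinical outcome measures are named alongside the MRI.

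No. 5 (Study Design and Procedures) says "Study design will be a Level I prospective randomized and blinded trial". It plans 20 patellar tendon and 20 hamstring autografts: "Patients undergoing ACL reconstruction with patellar and hamstring autografts will be randomized into 2 groups of 10 patients each". MRI is post-operative only, at 3, 6, 9 and 12 months, and yields mean T2 values. Surveys start before surgery and run for 2 years.

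No. 9 (Statistical Considerations) has two analysis commitments. The first covers everything: "Ranges, means and standard deviations for all measures will be determined and calculated". The second is "Common statistical procedures, such as ANOVA and analysis of covariance will be used to interpret changes in outcome variables", and that sentence goes on to limit itself to survey results followed over time. The comparative panel described in No. 8 sets individual, institutional and whole-registry outcomes against each other; the randomised arms are not mentioned.

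No section gives a significance level, effect size, power, precision target or confidence interval, or says how a null result would be read.

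**The concern.** The hypothesis is about a difference between arms in graft maturation, and the measure of maturation is T2 on MRI. Followed literally, No. 9 produces T2 means and SDs and stops there: no contrast between augmented and standard grafts, and no statement of how uncertain that contrast is. The procedures it names apply to surveys and are framed as change over time, so an arm comparison is not clearly specified there either.

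This matters because the trial is small. If the promised test is reported only as significant or not, a null result leaves the reader unable to tell a treatment that does nothing from one with a moderate benefit. An estimated difference with its interval shows what the data can and cannot exclude, which is the most a study of this size can offer on efficacy.

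**Working it through.** **The plan's own figure.** No. 5: 2 graft types x 2 arms x 10 patients = 40, which matches the total in Nos. 5 and 9. The count adds up, but it cannot be reproduced as a power or precision calculation because no inputs for one are given.

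**Inputs.** From No. 5: 20 v 20 with graft types combined, or 10 v 10 within one graft type. From No. 9: 40 completers. Assumed, because the documents are silent: two-sided 5% level, equal SDs, and true differences of 0.5 and 0.8 SD as examples. All results are in SD units.

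**Precision.** The 95% interval half-width is t(0.975, 2n-2) x sqrt(2/n).

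- 20 v 20: 2.024 x sqrt(2/20) = 2.024 x 0.3162 = 0.640 SD
- 10 v 10: 2.101 x sqrt(2/10) = 2.101 x 0.4472 = 0.940 SD
- 20 v 20 with the 36 df of a four-cell graft-by-arm model: 2.028 x 0.3162 = 0.641 SD

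So allowing for graft type costs almost nothing, while analysing each graft type alone widens the half-width from 0.64 to 0.94 SD.

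**Chance of a non-significant result.** One unadjusted two-sample t test, noncentral t with noncentrality d / sqrt(2/n):

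| True difference | Arms | Noncentrality | Power | Non-significant |
|---|---|---|---|---|
| 0.5 SD | 20 v 20 | 1.581 | 0.338 | 66% |
| 0.5 SD | 10 v 10 | 1.118 | 0.185 | 81.5% |
| 0.8 SD | 20 v 20 | 2.530 | 0.693 | 31% |
| 0.8 SD | 10 v 10 | 1.789 | 0.395 | 60% |

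**What an interval adds.** At 20 v 20, an observed difference of 0 gives -0.64 to +0.64 SD, which leaves a 0.5 SD benefit or harm open. An observed difference of 0.5 SD gives 0.5 - 0.64 = -0.14 to 0.5 + 0.64 = 1.14 SD. Both would be reported as non-significant, yet they say different things, and only the interval shows it.

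**Effect of baseline adjustment (surveys only).** With correlation r between the pre-operative and later score, the effective difference is d / sqrt(1 - r^2). At d = 0.5 and 20 v 20, power is 43% for r = 0.5, 58% for r = 0.7 and 73% for r = 0.8. At 10 v 10 it is 23%, 32% and 42%. T2 has no such gain available, since no pre-operative graft scan is planned.

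**The case against.** **A pilot needs no power calculation, may state a hypothesis, and Level I describes design rather than power.** All true. The point asks for no power calculation and no extra patients. It concerns the absence of a named comparison to answer the question that No. 2 asks.

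**ANOVA and ANCOVA can give contrasts with standard errors, and means with SDs by cell would let a reader work out a crude difference and interval.** This stands in part: the information would be recoverable if summaries were given by arm and graft type. What is missing is a commitment to report it. An adjusted difference could not be rebuilt from such summaries, and for T2 no model is named.

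**A reader might infer that the trial will most likely report no significant difference.** The documents do not support that. At a true 0.8 SD and 20 v 20, only 31% of single tests are non-significant. Strong baseline adjustment of surveys takes power at 0.5 SD above one half. There are also four scans: simulating them at 20 v 20 with 0.5 SD at each, and an assumed between-scan correlation of 0.3 to 0.7, at least one reaches p < 0.05 in about 57% to 71% of trials (about 13% to 18% with no effect at all). A bare test can therefore mislead in either direction.

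**A reader might infer that the plan sets a significance verdict, or will treat a null result as no effect.** It states no level, decision rule or such reading; it merely contains nothing that prevents one. Nor does any section propose using the SDs to size a later trial, so nothing here rests on that use.

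**Conclusion.** The point holds as a gap between aim and analysis. No. 2 promises a test of a between-arm effect on maturation; No. 9 commits to no augmented-versus-standard difference with its uncertainty, and offers T2 only descriptive summaries.

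Under the assumed level and equal SDs with all 40 analysed, the study can locate an arm difference to within about 0.64 SD overall or 0.94 SD within a graft type. The 66% and 81.5% figures apply to one unadjusted comparison with a true difference of 0.5 SD. They show why a bare test result would be uninformative; they do not forecast what the trial will report. The textual gap itself depends on none of these assumptions.

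**What to change.** In No. 9, state that the main result for the MRI T2 values and for each survey score is the augmented-minus-standard difference across both graft types, with its 95% confidence interval. Estimate it from a model with graft type as a factor and, for surveys, the pre-operative score as a covariate. Add that conclusions will rest on the interval and that a non-significant result will not by itself be reported as absence of effect. The ranges, means and SDs can stay as supporting summaries.

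In No. 2, describe the aim as estimating this difference in place of testing the hypothesis.

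This costs wording in two sections, with no added patients, visits or data. The downside is that the pilot gives up a yes/no verdict on its hypothesis. The change does not choose a leading measure or time point, so several intervals would still stand side by side; until one is chosen, all should be reported.
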